### 1.2 Study Design

This is a prospective, single-arm, multi-center clinical study designed to evaluate the intra-operative performance of the staple line reinforcement device in gastric and lung resection procedures in a post-market setting. Investigators are to perform the procedure using the device in compliance with their standard surgical approach and the ECHELON ENDOPATHTM Staple Line Reinforcement Device IFU.

Each site will utilize consecutive screening and enrollment in an effort to generate a random and representative patient population sample. Subjects will be consented and screened anytime during a period of 8 weeks prior to the date of surgery. Subjects will be considered treated when at least one ECHELON SLR has been placed during the procedure. Procedures will be performed per each institution's standard-of-care (SOC). All treated subjects will be followed post-operatively through discharge and again at 28, 70, and 135 days ( $\pm$  14 days) post-surgery. From the surgery date to study exit the duration will be approximately 19 weeks. Follow-up by phone for subjects is allowed when an on-site visit is not planned.

A minimum of 243 and a maximum of 431 eligible subjects are planned to be enrolled in up to 16 sites in the United States to ensure at least 112 subjects were treated for gastric procedures and at least 131 subjects were treated for lung resection procedures. An adaptive approach to sample size re-estimation will occur after approximately 50% of the originally planned sample size in each group has been enrolled.

### 2 Treatment Assignment

This is a single-arm study where all enrolled subjects will plan have the ECHELON SLR utilized during the surgical procedure.

### 3 Randomization and Blinding Procedures

As this is a single-arm study, no randomization will occur, and no blinding procedures are required.

### 4 Interval Windows

Interval windows will not be defined outside of those already specified in the protocol for visit scheduling. The final visit occurs approximately 19 weeks after surgery,. The protocol Schedule of Events specifies a window of 14 days around the scheduling of follow-up visits, and any information entered in the eCRFs at this visit will correspond to the associated visit. There will be no assigning of observations to time points outside of the visit to which they are recorded in the eCRFs. However, if an adverse event occurs at an unscheduled visit, it will be entered as a unscheduled visit.

### 5 Levels of Significance

Each of the two hypotheses will be evaluated using a one-sided significance level of 0.025 and the overall level of significance across the study will be controlled at a value that does not exceed 0.05. Estimation of all additional endpoints will be performed using 95% confidence intervals.

## 6 Analysis Sets

The summary of all performance and safety endpoints will be performed on the set of subjects in whom the ECHELON SLR is utilized during the surgical procedure. The summary of all primary and secondary endpoints will be performed by procedure group and in total.

### 7 Sample Size Justification

For the gastric procedure group, a sample size of at least 99 subjects is required to have a minimum of 80% power for rejecting the null hypothesis when the expected rate of the primary endpoint is 7% based on current available literature. Similarly, for the lung resection group, a sample size of at least 116 subjects is required to have a minimum of 80% power for rejecting the null hypothesis when the expected rate of the primary endpoint is 6% based on current available literature. Each calculation is determined using the Normal approximation with a one-sided significance level of 0.025 and makes the assumption of a 20% reduction in the expected rate of the primary endpoint with the ECHELON SLR. The performance goal-based hypotheses specified in Section 8.4.1 are based on establishing acceptable initial performance of the ECHELON SLR by ruling out a doubling of the expected risk that has been reported in the literature for these procedures. Accounting for an anticipated dropout rate as high as 12.5% in each procedure group leads to an initial planned sample size of 112 subjects in the gastric group and 131 subjects in the lung resection group.

Given the lack of available clinical data on the performance of the ECHELON SLR, an adaptive approach to sample size re-estimation will occur after approximately 50% of the originally planned sample size has been enrolled into each procedure group. The purpose of this interim analysis will be to estimate the rate of the primary endpoint in each group or concurrently to estimate the size of the relative reduction of this endpoint relative to the values reported in current literature. The current sample size calculation assumes an expected background rate of 7% in the gastric group, 6% in the lung resection group, and that a 20% relative reduction will be observed with the ECHELON SLR. Based on the values observed at the interim analysis time points for each group, the withingroup sample sizes will be re-estimated. A sample size of 200 subjects has been set as the maximum sample size that will be pursued following the interim analysis and sample size re-estimation process in the gastric group and a maximum of 231 subjects has been set in the lung resection group.

### 8 Analyses to be Conducted

#### 8.1 General Conventions

Categorical variables will be summarized descriptively by frequencies and associated percentages. Continuous variables will be summarized descriptively by number of subjects, mean, standard deviation, median, minimum, and maximum. Confidence intervals will also be provided for procedure-related variables.

Analyses will be conducted using SAS software. Analyses will be performed first using gastric data to populate tables and listing or parts of the tables and listing relevant to gastric. When the full data is available, a combined analyses (gastric and lung) will be conducted next. During the course of programming of tables that are mocked up in this SAP, minor modifications may become necessary. Examples of these minor modifications include, but are not limited to, re-wording of a footnote, addition of a footnote, re-labeling of a column, or addition or removal of a column from a listing. In

cases where modifications to tables or listings are not related to a change in statistical analysis methodology or conclusions that could be made on the originally proposed methodology, then no amendment of the SAP is necessary. Any final analyses that differ from what has been specified in this document will be identified within the final statistical output and documented within the clinical study report.

#### 8.2 Disposition of Study Subjects

Subject disposition will be summarized in total and by procedure group using counts and percentages. The number and percentage of subjects completed and discontinued will be tabulated along with specific reasons for discontinuation.

#### 8.3 Demographic, Baseline, and Surgical Characteristics

Summary statistics of subject demographics (age, gender, race, and ethnicity) will be presented in total and by procedure group. Similar summaries will also be provided in table and/or listing for baseline and surgical characteristics including but not limited to body mass index, surgical procedure, smoking history, ASA physical status classification, type of procedure conducted ,procedure duration,occurrence of blook transfusion, edocutter firing , air leak duration in lung resection.

#### 8.4 Primary and Secondary Endpoints and Associated Hypotheses

#### 8.4.1 Primary Endpoint and Associated Hypotheses

The primary endpoint for this study is the incidence of device-related AEs through the 70-day postprocedure follow-up visit. Specific device-related AEs that will be captured and counted toward the primary endpoint are listed below.

- Gastric
  - Bleeding (defined as below)
    - Occurrence of post-operative blood transfusion deemed related to bleeding at the staple line; or
    - Return to operating room before 70-day post-procedure follow-up visit due to bleeding deemed related to the staple line;
  - Leak (defined as below)
    - Occurrence of intra-operative or post-operative gastrointestinal leak related to the staple line as documented intra-operatively, by clinical exam, or radiographically;
  - Stricture (defined as below)
    - Occurrence of stricture documented radiographically or by endoscopy along the staple line;
- Lung Resection
  - Prolonged air leak deemed related to the staple line (defined as below)
    - Greater than postoperative day 7 (procedure=day 0);

- Empyema (defined as below)
  - Purulent fluid collection in the pleural space documented radiographically, excluding chronic empyema

The following hypotheses will be evaluated for the primary endpoint for gastric procedures:

H0: 
$$pG \ge 14.0\%$$

H1: pG < 14.0%

Where pG is the percentage of subjects experiencing at least one occurrence of bleeding, leak, or stricture through 70 days. A 95% confidence interval will be calculated for pG based on the sample proportion of subjects experiencing the endpoint using the Normal approximation to the Binomial distribution and the upper limit of this confidence interval will be compared to 14.0% to evaluate the above hypotheses. A p-value will be determined based on the same Normal approximation methodology.

A similar methodology will be applied to the data observed in lung procedures to evaluate the following hypotheses:

H0: 
$$pL \ge 12.0\%$$
  
H1:  $pL < 12.0\%$ 

Where pL is the percentage of subjects experiencing at least one occurrence of prolonged air leak or empyema through 70 days.

8.4.2 Secondary Endpoints and Associated Hypotheses

The secondary performance endpoints for this study are listed below.

- Number of study devices replaced during surgery due to slipping or bunching or not properly loaded onto stapler cartridge; and
- Device questionnaire by procedure group (gastric and lung resection) to capture usability.

8.4.3 Additional Endpoints

No additional endpoints defined for this study.

### 8.5 Safety Analyses

The primary safety endpoint in this study is the occurrence of device-related AEs. All device-related and procedure-related AEs reported during the study will be coded to MedDRA. All reported AEs will be summarized by MedDRA system organ class and preferred term by procedure group and in total. Separate summaries will be provided for device-related and procedure-related AEs. Serious AEs will be summarized in a similar manner. All adverse events considered unlikely, possibly, probably, or causally related to the device or the procedure will be collected during this study and are defined in the following subsections.

8.5.1 Adverse Event

An AE is defined as any untoward medical occurrence, regardless of its relationship to the study device or the study procedure. An untoward medical occurrence includes any new, undesirable

medical experience or worsening of a pre-existing condition, which occurs throughout the duration of the clinical study.

#### 8.5.2 Adverse Device Effect

An adverse device effect (ADE) is an AE related to the use of a study device. This includes any AE resulting from insufficient or inadequate IFU, deployment, implantation, installation, operation, or any malfunction of the study device. An ADE may also include any event resulting from user error or from intentional misuse of the study device

#### 8.5.3 Serious Adverse Event

It is the Investigator's responsibility to determine the "seriousness" of a reportable AE. A SAE is defined as an AE (as defined in Section 8.5.1) that results in any of the following:

- Death;
- A life-threatening illness or injury;
- A permanent impairment of a body structure or a body function;
- Required in-patient hospitalization or prolongation of existing hospitalization;
- Resulted in medical or surgical intervention to prevent life-threatening illness or injury or permanent impairment to a body structure or a body function; or
- Led to a fetal distress, fetal death, or a congenital abnormality or birth defect.

#### 8.5.4 Serious Adverse Device Effect (SADE)

A serious ADE (SADE) is an ADE that has resulted in any of the consequences characteristic of a SAE or that might have led to any of these consequences if suitable action had not been taken or intervention had not been made or if circumstance had been less opportune.

#### 8.5.5 Unanticipated Serious Adverse Device Effect (USADE)

An unanticipated serious adverse device effect (USADE) is an effect which, by its nature, incidence, severity or outcome, has not been identified. An anticipated SADE is an effect which by its nature, incidence, severity, or outcome, has been identified in the IFU

#### 8.6 Plans for Interim Analysis

One interim analysis in each procedure group is planned for sample size re-estimation. Details are provided in Section 7 above. Study enrollment may continue while the interim analysis is ongoing.

#### 8.7 Handling of Missing Data

All summaries will be performed only on subjects undergoing the scheduled procedure and only observed data will be summarized. There will be no imputation of data for early terminated subjects or for missing data within the database for the primary evaluation of the hypotheses specified above.

#### 8.8 Sensitivity Analysis

For subjects missing data at Visit 4 ( $70 \pm 14$  Days Post Procedure Follow Up visit), a sensitivity analysis will be conducted to evaluate whether the results hold under imputation using multiple imputation approach. A Fully Conditional Specification (FCS) method that employ conditional distribution of each primary endpoint variable will be implemented using proc mi to impute device specific AE at Visit 4. The following baseline variables: age, gender, and race, as well the the device-related and procedure-related AEs at Visit 2 (Procedure through discharge visit) will be used to inform the pattern of missingness. One hundred imputed datasets will be generated for each primary endpoint. SAS procedures genmod will be employed to obtain the relevantparameter estimates from each dataset. The resulting one hundred estimates for each primary endpoint will be combined using SAS procedure mianalyze.

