3.2.5 Removal of Subjects from Study

A subject has the right to withdraw from the study at any time for any reason without prejudice to his/her future medical care by the physician or the institution. Should a subject (or subject's legally authorized guardian/representative) decide to withdraw, 1) all data collected up to the point of withdrawal will be considered for analysis; and 2) all efforts will be made to collect and report the final visit observations as thoroughly and timely as possible. Participation may be terminated prior to completing the study for any of the reasons listed below (reasons that do not fit the categories below will be documented as "other").

Adverse Event

When the subject experiences an AE and the Investigator or Medical Monitor believes it is in the best interest of the subject to discontinue participation in the study, the subject will be withdrawn from the study.

Lost to follow-up

When contact with the subject has been lost without completing a final contact assessment, and every attempt to contact the subject has failed, the subject will be considered lost to follow-up. All attempts to contact the subject requesting his/her return for the final visit must be documented.

Withdrawal of consent

Any method of contact with the subject (or subject's legally authorized guardian/representative) in which he/she state they no longer want to participate in the study specific activities constitutes withdrawal of consent for participation in the study. When possible, the reason for withdrawal of consent will be documented.

Site Termination or Study Termination

A study site or the entire study may be terminated. When this occurs, all subjects currently enrolled at the site will be withdrawn and documented as early terminations. Reasons for site or study termination may include, but are not limited to the following:

- Administrative concerns (e.g., inadequate subject enrollment, Investigator/institution non-compliance, change of business strategy, etc.);
- Safety Issues, including those due to non-compliance, or those that substantially affect the risk to benefit ratio of the study subjects at a site or for the study as a whole; or
- Regulatory Body Mandate(s).

The Investigator has the right to terminate the subject's participation at any time. Should this be necessary, procedures for termination will be provided by the Sponsor.

Death

• When possible, the cause of death will be documented.

Other (which may include)

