5.9.6 Handling of Missing Data

All summaries will be performed only on subjects undergoing the scheduled procedure and only observed data will be summarized. There will be no imputation of data for early terminated subjects or for missing data within the database for the primary evaluation of the hypotheses specified above. Sensitivity analyses will be detailed in the SAP that will be designed to assess the robustness of the primary study conclusions to missing data or incomplete data on early terminated subjects.

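### The only missing-data sensitivity analysis (SAP 8.8) assumes data are missing at random; it cannot test loss driven by unrecorded events, and a tipping-point table is needed beside it

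*SAP*

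**What the plan says.** Protocol 5.9.6 and SAP 8.7 restrict the primary evaluation to observed data. SAP 8.7 states: "There will be no imputation of data for early terminated subjects". Protocol 5.9.6 leaves the robustness question to the SAP: "Sensitivity analyses will be detailed in the SAP that will be designed to assess the robustness of the primary study conclusions to missing data".

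SAP 8.8 answers with one analysis. For subjects missing data at Visit 4, "a sensitivity analysis will be conducted to evaluate whether the results hold under imputation using multiple imputation approach". The method is fully conditional specification in SAS with 100 imputed datasets. The predictors are age, gender, race, and the device- and procedure-related adverse events at Visit 2 (procedure through discharge). Visit 3 data and the reason for discontinuation are not in the model. No delta adjustment, worst case or tipping point is described.

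Protocol 3.2.5 lists the ways a subject can leave. One is an adverse event, at the discretion of the medical monitor or investigator: where either "believes it is in the best interest of the subject to discontinue participation in the study, the subject will be withdrawn from the study". Death is another. SAP Table 1 tabulates both as reasons for discontinuation. SAP 8.8 does not distinguish between them or any other reason.

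**The concern.** Imputation of this kind gives a subject who left the same later risk as a subject who stayed and looks alike on the listed predictors. The SAP does not use the term missing at random, but that is what the method assumes when no adjustment is added.

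Some exits in this study may be linked to the outcome. If a subject leaves and then has a leak, stricture or empyema that never reaches the database, the observed rate is too low. With a single arm and a fixed goal, nothing offsets that error: it moves the upper limit down, toward a pass. An analysis that borrows leavers' later risk from completers cannot show how much of this the conclusion could absorb.

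Deaths raise a separate question. The SAP does not say whether a death before Visit 4 counts as missing data at Visit 4. Read literally, with no exception stated, a random 70-day outcome would be drawn for a subject who had died.

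**Working it through.** **Inputs from the documents.**
- Goals: 14.0% gastric and 12.0% lung (SAP 8.4.1).
- Significance: "Each of the two hypotheses will be evaluated using a one-sided significance level of 0.025" (SAP 5), so z = 1.96.
- Design rates: the plan "assumes an expected background rate of 7% in the gastric group, 6% in the lung resection group" and "makes the assumption of a 20% reduction in the expected rate of the primary endpoint with the ECHELON SLR" (SAP 7). These give 0.8 × 7% = 5.6% and 0.8 × 6% = 4.8%.
- Sample sizes: 99 and 116 evaluable, 112 and 131 planned, dropout as high as 12.5% (SAP 7).

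**Reproducing the plan's figures.** For gastric, "a sample size of at least 99 subjects is required to have a minimum of 80% power for rejecting the null hypothesis". A one-sample z test using the variance under the null rejects at 7 or fewer of 99 events, because (7/99 − 0.14)/√(0.14 × 0.86/99) = −1.99. At a true rate of 5.6%, P(X ≤ 7) = 0.809. For lung, the test rejects at 7 or fewer of 116 (z = −1.98), and at 4.8% P(X ≤ 7) = 0.806. Both stated sizes reproduce. The planned totals follow as 99 × 1.125 = 111.4, rounded up to 112, and 116 × 1.125 = 130.5, rounded up to 131.

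**Loss at the ceiling.** Gastric: 0.125 × 112 = 14 missing, 98 observed. Lung: 0.125 × 131 = 16.4, taken as 16 missing, 115 observed. I assume that all this loss occurs before Visit 4, that the missing subjects have no recorded event, and that the primary denominator is the observed subjects.

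**Pass limits, Wald interval.** Upper limit = p + 1.96 × √(p(1 − p)/n).

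| Group | Set | Largest passing count (upper limit) | Next count (upper limit) |
|---|---|---|---|
| Gastric, 14.0% | observed, n = 98 | 8 (13.6%) | 9 (14.9%) |
| Gastric, 14.0% | all treated, n = 112 | 9 (13.1%) | 10 (14.2%) |
| Lung, 12.0% | observed, n = 115 | 8 (11.6%) | 9 (12.7%) |
| Lung, 12.0% | all treated, n = 131 | 9 (11.2%) | 10 (12.2%) |

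**Tipping counts.** In both groups the full treated set fails at 10 events, so the tipping count is 10 minus the observed events.

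| Observed events | Missing events that overturn the pass | Gastric: observed rate, implied rate in missing | Lung: observed rate, implied rate in missing |
|---|---|---|---|
| 5 | 5 | 5.1%, 5/14 = 36% | 4.3%, 5/16 = 31% |
| 6 | 4 | 6.1%, 4/14 = 29% | 5.2%, 4/16 = 25% |
| 7 | 3 | 7.1%, 3/14 = 21% | 6.1%, 3/16 = 19% |
| 8 | 2 | 8.2%, 2/14 = 14% | 7.0%, 2/16 = 12.5% |

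At the design rates the expected observed count is 98 × 0.056 = 5.5 gastric and 115 × 0.048 = 5.5 lung, so the table starts close to what the plan expects. At the extreme, 5/98 with all 14 missing counted as events is 19/112 = 17.0%, upper limit 23.9%.

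**Other reading of the normal approximation.** With the null-variance test that reproduces 99 and 116, the limits are 6/98 and 8/112 gastric (z = −2.25, −2.09), and 6/115 and 8/131 lung (z = −2.24, −2.08). The tipping count is then 9 minus the observed events: 4 for a pass with 5, and 3 for a pass with 6.

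**The case against.** **The imputation is not empty.** Visit 2 adverse events are predictors, so loss explained by in-hospital events is partly handled. This stands. It would be too strong to say that SAP 8.8 cannot reveal any informative loss. What it cannot test is loss that depends on events never recorded.

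**A reader might infer that the imputation will almost always repeat the completers' verdict.** The documents do not support that. In simulation it held only for an imputation model without predictors, pooled on the proportion scale (99.7–99.8% agreement). With predictors like those in SAP 8.8, under assumed prevalences and associations, agreement ranged from roughly three quarters to nearly all trials. This does not vindicate the check: disagreement also arose when loss was non-informative, which points to imputation noise with few events.

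**A reader might also infer a probability of a wrong pass.** Suppose leavers carry three times the completers' risk, the overall gastric rate is exactly 14%, and every leaver's event is lost. The completers' rate is then 14/(0.875 + 3 × 0.125) = 11.2%, and P(X ≤ 8 of 98) = 21.8%. The factor of three is not in the documents. Protocol 3.2.5 keeps data collected up to withdrawal, so events before exit are not lost. With the null-variance limit of 6, the figure is 6.8%. No such probability should be attached to this point.

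**The 12.5% is a ceiling and is not tied to day 70.** This stands. Follow-up runs to day 135, Visit 4 may be by telephone, and Protocol 3.2.5 asks for every effort to obtain final observations. Actual loss by Visit 4 may be smaller, and the tipping counts would change with it.

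**The protocol's commitment.** Protocol 5.9.6 promises sensitivity analyses for missing data and does not specify a not-at-random one. SAP 8.8 supplies one analysis, so a charge that the promise is broken goes too far.

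**Readers could do the sums themselves.** SAP Tables 1 and 17 would let a reader approximate the tipping arithmetic. They would not show which missing subjects already had an event, and the plan does not commit to reporting the result.

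**Conclusion.** The point holds in a bounded form. SAP 8.8 is the only missing-data sensitivity analysis, it is missing-at-random in form, and it leaves the direction of error that favours the device untested. At the planned dropout ceiling, passes with 5 to 8 observed events would be overturned by 5 down to 2 events among 14 gastric or 16 lung missing subjects. The first case needs a rate in the missing about seven times the observed rate (36% against 5.1%, gastric). The last needs less than twice (14% against 8.2%). The plan as written would not tell a reader which case applies.

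These counts rest on the Wald interval, on loss of 12.5% before Visit 4, and on no recorded event among the missing. They do not depend on any assumed risk in leavers. That deaths and adverse-event withdrawals would be imputed is inferred from the absence of an exception in SAP 8.8, not from a statement. The primary analysis itself need not change, but the addition should be made before the results are known.

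**What to change.** In SAP 8.8, add a tipping-point table for each procedure group:

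1. Count any endpoint event recorded before exit as an event.
2. Among treated subjects with no recorded event and no 70-day status, vary the number with an event from 0 to all.
3. Apply the primary interval to the full treated set each time.
4. Report the smallest number, and the implied rate in the missing, at which the upper limit reaches 14.0% or 12.0%, beside the observed rate.

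State that outcomes are not imputed for deaths before Visit 4. Score them from the adverse event record using the existing endpoint definitions, and as the extreme case count all of them as events. Keep the present imputation as the missing-at-random reference.

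The cost is a few sentences and one extra table, with no new data or subjects. The downside for the sponsor is that a pass which few missing events could overturn must be reported as fragile.

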3.5 SCHEDULE OF EVENTS

Table 1: Schedule of Events

	Visit 1	Visit 2	Visit 3	Visit 4	Visit 5	
Activity	Screening Visit (-56 to -1 Days) ^a	Procedure (Day 0) Through Discharge Visit	Post Procedure Follow Up Visit (28 ± 14 Days) ^b	Post Procedure Follow Up Visit (70 ± 14 Days) ^b	Post Procedure Follow Up Visit (135 ± 14 Days) ^b	Unscheduled Visit, if applicable ^a
Informed consent	X					
Demographics (age, gender, race, and ethnicity)	Х					
Height and weight (both with no shoes)	Х					
Medical and surgical history (including diagnosis)	Х	х				
Review of inclusion/exclusion criteria	Х	х				
Surgical data collected for evaluation		х				
Collect device questionnaire°		X				
Concomitant procedures conducted in addition to study procedure		x	Х	Х	х	х
Concomitant medications (30 days prior)	Х	х	Х	Х	х	х
Device-related and procedure-related AEs		х	Х	Х	Х	х
Video Assessment ^d		X				
Unscheduled visits (if applicable)						х
Subject completion/discontinuation		Х	Х	Х	Х	Х

The screening activities will occur prior to the study procedure and may be completed on the day of the procedure;

AE = adverse events

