| Listing 8  | Malignancy Form
All Subjects                            |
| Listing 9  | Neo-Adjuvant Chemotherapy
All Subjects                  |
| Listing 10 | Neo-Adjuvant Radiation
All Subjects                     |
| Listing 11 | Inclusion/Exclusion Criteria Procedure Day
All Subjects |
| Listing 13 | Intraoperative Data
All Subjects                        |
| Listing 14 | Endocutter Firing
All Subjects                          |
| Listing 15 | Intervention for Intraoperative Bleeding
All Subjects   |

| Listing 16 | Chest Tube Summary
All Subjects                               |
|------------|--|
| Listing 17 | Air Leak Information
All Subjects                             |
| Listing 18 | Lung Resection Assessment
All Subjects                        |
| Listing 19 | Device Questionnaire
All Subjects                             |
| Listing 20 | Gastric Primary Assessment (Pre-Discharge)
All Subjects       |
| Listing 21 | Additional Intraoperative Details – Gastric Only
All Subjects |
| Listing 22 | Unscheduled Visit
All Subjects                                |
| Listing 23 | Discharge
All Subjects  |
| Listing 24 | Gastric Primary Assessment (Post-Discharge)
All Subjects      |
| Listing 25 | Post-Procedure Follow-Up
All Subjects                         |
| Listing 26 | Adverse Events
All Subjects                                   |
| Listing 27 | Concomitant Procedures
All Subjects                           |
| Listing 28 | Concomitant Medications
All Subjects                          |
| Listing 29 | Protocol Deviations
All Subjects                              |
| Listing 30 | Radiation Therapy
All Subjects                                |

| Listing 31 | Blood Transfusion Detail
All Subjects           |
|------------|--|
| Listing 32 | Subject Completion/Discontinuation
All Subjects |

Programmin note: Listign for Gastric will be generated first. The Lung Resection listing will be generated when all data is available.

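### SAP 8.8 imputes the Visit 4 outcome without stating that a qualifying event already recorded stays a yes, and it makes no use of Visit 3

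*SAP*

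**What the plan says.** SAP 8.8 applies to subjects with no Visit 4 data. It uses fully conditional specification with 100 imputed datasets "to impute device specific AE at Visit 4". The predictors are age, gender and race, and "the device-related and procedure-related AEs at Visit 2 (Procedure through discharge visit) will be used to inform the pattern of missingness". Visit 3 events and events at unscheduled visits are not listed.

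The endpoint is cumulative. SAP 8.4.1 counts a gastric subject with "at least one occurrence of bleeding, leak, or stricture through 70 days"; the lung endpoint is built the same way from prolonged air leak and empyema.

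The data exist. In Protocol 3.5 the row "Device-related and procedure-related AEs" is marked for Visits 2 to 5 and for unscheduled visits, and Protocol 6.4.1 records onset dates.

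Three other places bear on the point:
- SAP 8.7 runs the primary test on observed data with no imputation.
- Protocol 3.2.5 says that for withdrawn subjects "all data collected up to the point of withdrawal will be considered for analysis".
- SAP 4 says: "There will be no assigning of observations to time points outside of the visit to which they are recorded in the eCRFs".

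Protocol 5.9.6 left it to the SAP to give sensitivity analyses "designed to assess the robustness of the primary study conclusions to missing data or incomplete data on early terminated subjects". Section 8.8 is the only one in the SAP, and the appendix has no table shell for it.

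**The concern.** A subject with a leak recorded at Visit 3 who then misses Visit 4 has a known 70-day outcome. Taken literally, 8.8 treats that subject as missing and draws the outcome. Because the model contains no information after discharge, the recorded leak does not even raise the chance that the draw is a yes. Subjects with complications may also be the ones who stop attending, and this analysis is meant to guard against exactly that.

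The same literal rule errs in the other direction too. A subject seen event-free at Visit 3 is drawn with risk for the whole 70 days, part of which has already passed without an event.

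At stake is the plan's only check on the anticipated dropout of up to 12.5%. Two programmers could obtain different sensitivity results from the same data. The section also examines no departure from its own missing-data assumption.

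**Working it through.** **Inputs.** SAP 7: planned N 112 gastric and 131 lung, dropout up to 12.5%, expected rates 7% and 6% with a 20% reduction (5.6% and 4.8%). SAP 8.4.1: goals 14% and 12%, Normal-approximation 95% interval. Section 8.8 states no figure to reproduce. The sample sizes it rests on do reproduce: 99 × 1.125 = 111.4, so 112; 116 × 1.125 = 130.5, so 131. Loss of 12.5% is 14 of 112 (98 observed) and about 16 of 131 (115 observed).

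**Step 1: keep or replace one recorded event.** Event counts are assumed. Let x events occur in n observed subjects, with N − n lost. Of the lost, k have a recorded event that is kept, and j = N − n − k are drawn with probability q = x/n (predictors taken as uninformative).
- P = (x + k + jq)/N
- Within variance U = P(1 − P)/N
- Between variance B = [jq(1 − q) + j²q(1 − q)/n]/N²
- Upper limit = P + 1.96 √(U + 1.01B), for 100 imputations

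Replacing the event means k = 0.

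Gastric, x = 8, n = 98:
- Replaced: P = 8/98 = 8.16%, U = 0.000669, B = 0.0000956, upper limit 13.6%. Meets 14%.
- Kept: P = (8 + 1 + 13 × 0.0816)/112 = 8.98%, U = 0.000730, B = 0.0000880, upper limit 14.6%. Fails.

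Lung, x = 8, n = 115:
- Replaced: P = 8/115 = 6.96%, upper limit 11.6%. Meets 12%.
- Kept: P = (8 + 1 + 15 × 0.0696)/131 = 7.67%, upper limit 12.5%. Fails.

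**Step 2: how many such subjects are needed (gastric).**

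| Observed events in 98 | Recorded events in lost subjects | Replaced | Kept |
|---|---|---|---|
| 8 | 1 | 13.6% | 14.6% |
| 7 | 2 | 12.2% | 14.3% |
| 6 | 3 | 10.9% | 14.04% |
| 5 | 4 | 9.5% | 13.8% (no reversal) |

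The planned rate gives 5.6% × 112 = 6.3 events, so the row with 6 is the relevant one.

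**Step 3: how far Step 1 depends on q.** The 13 other lost gastric subjects were drawn at 8.2% each. If none of them has an event, the kept result is 9/112 = 8.04%, upper limit 0.0804 + 1.96 √(0.0804 × 0.9196/112) = 13.07%, which passes. With the parameter-uncertainty term scaled by the square of the ratio of q to x/n, the limit is 13.99% at q = 4.9% and 14.14% at q = 5.7%. The reversal therefore needs the remaining risk to be more than about 60% of the observed rate. That is plausible for subjects lost soon after discharge and less so for those lost after Visit 3.

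**Step 4: average effect.** Assume a true gastric rate of 14%, events split 40/40/20% (by discharge, to Visit 3, after), and all 12.5% lost after Visit 3. Let dropout be d for most subjects and r × d for those with an event between discharge and Visit 3, and let a Visit 2 event carry through as a yes. Then d = 0.125/(0.944 + 0.056r). Among subjects without a Visit 2 event the observed rate is e = [0.056(1 − rd) + 0.028(1 − d)] / [0.056(1 − rd) + 0.888(1 − d)], and the imputed rate is 0.056 + 0.944e.
- r = 1: d = 0.125, e = 0.0890, result 14.0%.
- r = 2: d = 0.1184, e = 0.0674/0.8256 = 0.0817, result 13.3%.
- r = 3 and r = 4: 12.7% and 12.1%.

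In simulation with recorded events kept and only unknown status imputed, the mean is 13.9 to 14.2%. The documents give no value for r.

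**Step 5: tipping point.** Count all treated subjects and ask how many of those lost event-free would need an unseen event. Gastric, 6 observed and 14 lost: 9/112 gives 13.07% (passes), 10/112 gives 14.21% (fails). Lung, 6 observed and 16 lost: 9/131 gives 11.20% (passes), 10/131 gives 12.18% (fails). In both groups the result holds with up to 3 unseen events and fails at 4. This differs from the Step 2 row with 6 events because Step 2 also imputes the remaining 11 subjects.

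**The case against.** The best reply is that 8.8, read with the rest of the plan, already implies the right answer. It describes the imputed quantity as a primary endpoint variable, and 8.4.1 defines that endpoint cumulatively. A subject with a recorded leak therefore has no missing value. SAP 8.7 summarises observed data, Protocol 3.2.5 uses data up to withdrawal, and deleting a known yes would not test whether the primary result holds. A careful programmer would keep it. This stands, and it limits the point to a literal application of 8.8. But 8.8 is the operative instruction: it selects subjects by a missed visit rather than by unknown outcome, and it never says that recorded events are held.

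The effect is also small at the design rate. With the Step 4 split, about 112 × 0.056 × 0.4 × 0.125 = 0.3 gastric subjects would have a replaceable event between discharge and Visit 3 if dropout is unrelated to events, and about 0.6 at a ratio of 2, against the three needed. The 12.5% is a ceiling, and telephone follow-up is allowed. This stands too.

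A reader might infer that 8.8 imputes only the interval ending at Visit 4, so that someone lost before Visit 3 receives no risk for the gap. The reference to primary endpoint variables makes that reading strained. A reader might also take SAP 4 as forbidding earlier events from counting at day 70. It is a visit-window rule; read that way, the primary endpoint itself could not be built.

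**Conclusion.** The point holds as a defect in the wording and design of the only missing-data sensitivity analysis. Applied literally, 8.8 can replace a known event with a draw, ignores what Visit 3 shows, and tests no departure from its own assumption.

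Its size is modest. One recorded event in a lost subject can reverse the sensitivity result when 8 events are observed, if the other lost subjects are drawn at or near the observed rate; three are needed at 6 observed gastric events. These counts, the event split and the dropout ratios are assumptions.

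Two stronger conclusions are not supported. The primary test is not affected, because SAP 8.7 excludes imputation from it. Nor does 8.8 always understate the rate: if dropout is unrelated to events, the literal rule gives 14.0% on average for a true 14%, because replaced events and excess risk given to event-free subjects offset each other. The downward shift appears only if subjects with events drop out more often.

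**What to change.** Amend SAP 8.8 as follows.
1. Set the 70-day endpoint to yes for any qualifying event observed through day 70, whichever visit recorded it, unscheduled visits included.
2. Impute only subjects who were event-free at last contact and whose 70-day status is unknown. Impute over the whole unobserved period, with the model conditioned on being event-free up to that contact. Visit 3 then enters as the known status at day 28. Keep the model simple, because events are few.
3. Report the tipping-point count for each group beside the imputed result, and add a table shell.

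No new data are needed: adverse events are collected at Visit 3 and at unscheduled visits, and onset dates are recorded. The cost is a few sentences, one table and a little more programming. The drawback is that the last interval will hold few events. With the assumed split and the planned rate, about 0.056 × 0.2 × 98 = 1.1 gastric events are expected after Visit 3 among completers, so covariates will often not be estimable there.
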